7.3 Other Assessments

7.3.1 Photography

Standardized digital photographs will be taken of the subject's lateral canthus region, glabellar region, and the full face at baseline (prior to treatment) and at each post-treatment visit.

Each Investigator (or designee) will take photographs using identical camera equipment, conditions, and settings. Detailed instructions for photography will be provided in a separate photography manual.

7.3.2 Pregnancy Test

For females of childbearing potential, a urine pregnancy test will be performed prior to treatment at screening, baseline (prior to treatment) and Month 6/ET. A negative pregnancy test is required for study inclusion. The result will be documented.

7.4 Appropriateness of Measurements

The efficacy and safety measurements used in this study are considered standard measurements, and are generally recognized as reliable, accurate, and relevant. The validated 4-point Photographic Scale of Glabellar Line Severity has been chosen in agreement with the FDA. A similar scale has been developed for LCL in accordance with FDA guidance.

8. CLINICAL STUDY VISITS DESCRIPTIONS AND PROCEDURES

8.1 Description of Clinical Study Visits

Please refer to the Schedule of Assessments [Table 2](#).

A written, signed ICF (inclusive of HIPAA and photo consent) must be obtained prior to performing any clinical study-related evaluations and/or procedures. The subject must be provided with a fully completed, dated and signed copy.

8.1.1 Screening/Visit 1 (-14 days to Day 0)

The screening and baseline visits may be performed on the same day; however, a maximum of 14 days is allowed between the screening and baseline visits.

 GALDERMA	Title 43QMI902 Clinical Study Protocol - QM1114 - LCL and GL	Doc id MA-40371
--	---	----------------------------------

At the screening visit, the Investigator or designee will:

1. Review and explain the nature of the study to the subject, particularly the prohibited activities and constraints (e.g., restrictions for other aesthetic treatments and the use of topical and systemic medications, see Section [5.4.5](#)).
2. Obtain the signed and dated ICF (inclusive of HIPAA and photo consent); provide a fully completed dated and signed copy to the subject.
3. Collect information regarding demographics (i.e., date of birth, gender, race, ethnicity, height, and weight), Fitzpatrick skin type, relevant medical history and concurrent diseases, previous facial treatments/procedures (including toxin naïve/non-toxin naïve), previous medications and procedures, and concomitant medications and procedures (see [Table 2 Schedule of Assessments](#)).
4. Instruct the subject on how to complete the LCL-SLA at **CCI** maximum smile. Subject to complete self-assessments using the 4-point Photographic Scales (LCL-SLA). LCL severity of Level 2 or Level 3 on the LCL-SLA at maximum smile, as assessed by the subject, is required for study inclusion. (Section [7.1.2](#) and [Appendix 2](#))
5. Instruct the subject on how to complete the GL-SLA at maximum frown. Subject to complete self-assessment using the Static 4-point Categorical Scales (GL-SLA). Moderate to severe GL (score of 2 or 3 on the Static 4-point Categorical Scale) at maximum frown, as assessed by the subject, is required for study inclusion. (Section [7.1.4](#))
6. Investigator to complete assessment of the subject's bilateral LCL severity at **CCI** maximum smile using the 4-point Photographic Scales (LCL-ILA). Moderate to severe bilaterally symmetrical LCL (grade 2 or 3 on the LCL-ILA) at maximum smile, as assessed by the Investigator, is required for study inclusion. (Section [7.1.1](#) and [Appendix 1](#))
7. Investigator to complete assessment of the subject's GL severity at **CCI** maximum frown using the 4-point Photographic Scales (GL-ILA). Moderate to severe GL (grade 2 or 3 on the 4-point Photographic Scale) at maximum frown, as assessed by the investigator, is required for study inclusion. (Section [7.1.3](#) and [Appendix 3](#))
8. Investigator to perform a focused PE. ([Appendix 6](#)). Record abnormal findings as medical history. Clinically significant abnormal findings are exclusionary; document as screen fail and do not enrol the subject in the study.
9. If the subject is a female of childbearing potential, collect urine for UPT and complete pregnancy test (see laboratory manual for additional procedures). Document the result. A negative result is required for study inclusion.
10. Record any AEs on the eCRF. AEs will be collected starting from the time of Informed Consent signature.
11. Review the inclusion/exclusion criteria, and confirm if subject meets study eligibility requirements.
 - If yes, schedule the baseline visit.
 - If no, document the subject as a screen failure.

 GALDERMA	Title 43QMI902 Clinical Study Protocol - QM1114 - LCL and GL	Doc id MA-40371
--	---	----------------------------------

12. For all subjects, enter the subject information into the eCRF; a SIN will be assigned via the eCRF system.

8.1.2 Baseline/Visit 2 [Day 0]

If the screening and baseline visits are performed as on same day, only perform study assessments once (i.e., AE, concomitant therapies/procedures, UPT, PE, SLA, ILA, inclusion/exclusion review). A maximum of 14 days is allowed between the screening and baseline visits.

At the baseline visit, the Investigator or designee will:

1. Ask the subject about AEs using an open-ended question, such as "Have you noticed any change in your health since the last visit?" Record all events, as appropriate.
2. Ask the subject about any changes in his/her concomitant therapies/procedures (added, removed or changed) since the previous visit. Record all changes.
3. **CCI**
[REDACTED]
4. Instruct the subject on how to complete the LCL-SLA at **CCI** maximum smile. Subject to complete the self-assessments using the 4-point Photographic Scales (LCL-SLA). LCL severity of level 2 or 3 on the 4-point Photographic Scale at maximum smile, as assessed by the subject, is required for study inclusion. (Section 7.1.2 and [Appendix 2](#))
5. Instruct the subject on how to complete the GL-SLA at maximum frown. Subject to complete the self-assessment using the Static 4-point Categorical Scale (GL-SLA). Moderate to severe GL (grade of 2 or 3 on the Static 4-point Categorical Scale) at maximum frown, as assessed by the subject, is required for study inclusion. (Section 7.1.4)
6. Investigator to complete assessment of the subject's LCL severity at **CCI** maximum smile using the 4-point Photographic Scales (LCL-ILA). Moderate to severe LCL (grade 2 or 3 on the 4-point Photographic Scale) at maximum smile, as assessed by the investigator, is required for study inclusion.
7. Investigator to complete assessment of the subject's GL severity at **CCI** maximum frown using the 4-point Photographic Scales (GL-ILA). Moderate to severe GL (grade of 2 or 3 on the 4-point Photographic Scale) at maximum frown, as assessed by the investigator, is required for study inclusion. (Section 7.1.3 and [Appendix 3](#))
8. **CCI**
[REDACTED]
9. Obtain the subject's vital signs (blood pressure, heart rate, and respiratory rate). Vital signs are to be taken seated after 10 minutes rest (Section 7.2.2).
10. Obtain 12-lead ECG recording after the subject has been resting in a supine position for at least 10 minutes ([Section 7.2.3](#)).
11. If the subject is a female of childbearing potential, collect urine for UPT and complete pregnancy test (see laboratory manual for additional procedures). Document the result. A negative result is required for study inclusion.

 GALDERMA	Title 43QMI902 Clinical Study Protocol - QM1114 - LCL and GL	Doc id MA-40371
--	---	----------------------------------

12. Collect blood sample (chemistry and hematology) for analysis at the central laboratory ([Section 7.2.4](#)).
13. Collect blood sample for neutralizing antibody testing ([Section 7.2.5](#)).
14. Take subject photographs (refer to photo manual for complete instructions). If the subject is wearing make-up, instruct the subject to remove it prior to taking photographs.
15. Investigator to perform a focused PE. ([Appendix 6](#)). Clinically significant abnormal findings are exclusionary; document as screen fail and do not enroll the subject in the study.
16. Review the inclusion/exclusion criteria, and confirm if subject meets study eligibility requirements.
 - If yes, enroll/randomize the subject in the clinical study. Proceed to next steps.
 - If no, document the subject as a screen failure.
17. For all subjects, enter appropriate data into the eCRF; the SIN should have been assigned via the eCRF system at the screening visit
18. For subjects who meet all eligibility requirements, the Investigator or designee will receive notification of the subject's kit number/randomization assignment once all required data is entered into the eCRF. The Investigator or designee should prepare the assigned treatment accordingly and complete the required documentation and eCRF. ([Section 6.1.7](#)).
19. Prior to injection, clean the subject's treatment areas with a suitable antiseptic solution.
20. The Investigator will administer the assigned treatments. See [Section 6.1.7.1](#) for injection technique and treatment procedure requirements. Following treatment administration, subjects will be monitored at the study center for 30 minutes. ([Section 6.1.7.2](#))
21. Obtain the subject's post-treatment vital signs (blood pressure, heart rate, and respiratory rate). Vital signs are to be taken seated after 10 minutes after injection ([Section 7.2.2](#)).
22. **CCI**
23. Ask the subject about AEs using an open-ended question. Record all events, as appropriate, on the corresponding eCRF form(s).
24. Record post-treatment concomitant therapies/procedures.
25. Schedule the next visit (Day 7 \pm 1 day).

8.1.3 Day 7/Visit 3 (\pm 1 day)

The Investigator or designee will:

1. Ask the subject about AEs using an open-ended question, such as "Have you noticed any change in your health since the last visit?" Record all events, as appropriate.
2. Ask the subject about any changes in his/her concomitant therapies/procedures (added, removed or changed) since the previous visit. Record all changes.
3. **CCI**

 GALDERMA	Title 43QMI902 Clinical Study Protocol - QM1114 - LCL and GL	Doc id MA-40371
--	---	----------------------------------

4. Instruct the subject on how to complete the LCL-SLA at **CCI** maximum smile. Subject to complete self-assessments using the 4-point Photographic Scale (LCL-SLA). (Section 7.1.2 and [Appendix 2](#))
5. Instruct the subject on how to complete the GL-SLA at maximum frown. Subject to complete self-assessment of GL severity at maximum frown using the Static 4-point Categorical Scale. (Section 7.1.4)
6. **CCI**
- 7.
8. Obtain the subject's vital signs (blood pressure, heart rate, and respiratory rate). Vital signs are to be taken seated after 10 minutes rest (Section 7.2.2).
9. Take subject photographs (refer to photo manual for complete instructions). If the subject is wearing make-up, instruct the subject to remove it prior to taking photographs.
10. Investigator to complete assessment of the subject's bilateral LCL severity at **CCI** maximum smile using the 4-point Photographic Scale (LCL-ILA). (Section 7.1.1 and [Appendix 1](#))
11. Investigator to complete assessment of the subject's GL severity at **CCI** maximum frown using the 4-point Photographic Scale (GL-ILA). (Section 7.1.3 and [Appendix 3](#))
12. Investigator to perform a focused PE. ([Appendix 6](#))
13. Schedule the next visit (Day 14 ±3 days).

8.1.4 Day 14/Visit 4 (±3 days)

The Investigator or designee will:

1. Ask the subject about AEs using an open-ended question, such as "Have you noticed any change in your health since the last visit?" Record all events, as appropriate.
2. Ask the subject about any changes in his/her concomitant therapies/procedures (added, removed or changed) since the previous visit. Record all changes.
3. Instruct the subject on how to complete the LCL-SLA at **CCI** maximum smile. Subject to complete self-assessment of bilateral LCL severity the 4-point Photographic Scale. (Section 7.1.2 and [Appendix 2](#))
4. Instruct the subject on how to complete the GL-SLA at maximum frown. Subject to complete self-assessment of GL severity using the Static 4-point Categorical Scale. (Section 7.1.4)
5. **CCI**
- 6.

 GALDERMA	Title 43QMI902 Clinical Study Protocol - QM1114 - LCL and GL	Doc id MA-40371
--	---	----------------------------------

Effective date: 2020-06-09 07:02

Effective

Version: 4.0

7. Obtain the subject's vital signs (blood pressure, heart rate, and respiratory rate). Vital signs are to be taken seated after 10 minutes rest (Section 7.2.2).
8. Take subject photographs (refer to photo manual for complete instructions). If the subject is wearing make-up, instruct the subject to remove it prior to taking photographs.
9. Investigator to complete assessment of the subject's bilateral LCL severity at **CCI** [REDACTED] maximum smile using the 4-point Photographic Scale (LCL-ILA). (Section 7.1.1 and [Appendix 1](#))
10. Investigator to complete assessment of the subject's GL severity at **CCI** [REDACTED] maximum frown using the 4-point Photographic Scale (GL-ILA). (Section 7.1.3 and [Appendix 3](#))
11. Investigator to perform a focused PE. ([Appendix 6](#))
12. Schedule the next visit (Month 1 \pm 5 days).

8.1.5 Month 1/Visit 5 (\pm 5 days)

The Investigator or designee will:

1. Ask the subject about AEs using an open-ended question, such as "Have you noticed any change in your health since the last visit?" Record all events, as appropriate.
2. Ask the subject about any changes in his/her concomitant therapies/procedures (added, removed or changed) since the previous visit. Record all changes.
3. Instruct the subject on how to complete the LCL-SLA at **CCI** [REDACTED] maximum smile. Subject to complete self-assessment of bilateral LCL severity using the 4-point Photographic Scale. (Section 7.1.2 and [Appendix 2](#))
4. Instruct the subject on how to complete the GL-SLA at maximum frown. Subject to complete self-assessment of GL severity using the Static 4-point Categorical Scale. (Section 7.1.4)
5. **CCI** [REDACTED]
6. [REDACTED]
7. [REDACTED]
8. Obtain the subject's vital signs (blood pressure, heart rate, and respiratory rate). Vital signs are to be taken seated after 10 minutes rest (Section 7.2.2).
9. Obtain 12-lead ECG recording after the subject has been resting in a supine position for at least 10 minutes (Section 7.2.3).
10. Collect blood sample for neutralizing antibody testing (Section 7.2.5).
11. Take subject photographs (refer to photo manual for complete instructions). If the subject is wearing make-up, instruct the subject to remove it prior to taking photographs.

 GALDERMA	Title 43QMI902 Clinical Study Protocol - QM1114 - LCL and GL	Doc id MA-40371
--	---	----------------------------------

12. Investigator to complete assessment of the subject's bilateral LCL severity at **CCI** maximum smile using the 4-point Photographic Scale (LCL-ILA). (Section [7.1.1](#) and [Appendix 1](#))
13. Investigator to complete assessment of the subject's GL severity at **CCI** maximum frown using the 4-point Photographic Scale (GL-ILA). (Section [7.1.3](#) and [Appendix 3](#))
14. Investigator to perform a focused PE. ([Appendix 6](#))
15. Schedule the next visit (Month 2 \pm 5 days).

8.1.6 Months 2-5/Visit 6-9 (\pm 5 days)

The Investigator or designee will:

1. Ask the subject about AEs using an open-ended question, such as "Have you noticed any change in your health since the last visit?" Record all events, as appropriate.
2. Ask the subject about any changes in his/her concomitant therapies/procedures (added, removed or changed) since the previous visit. Record all changes.
3. Instruct the subject on how to complete the LCL-SLA at **CCI** maximum smile. Subject to complete self-assessment of bilateral LCL severity using the 4-point Photographic Scale. (Section [7.1.2](#) and [Appendix 2](#))
4. Instruct the subject on how to complete the GL-SLA at maximum frown. Subject to complete self-assessment of GL severity using the Static 4-point Categorical Scale. (Section [7.1.4](#))
5. **CCI**
- 6.
- 7.
8. Take subject photographs (refer to photo manual for complete instructions). If the subject is wearing make-up, instruct the subject to remove it prior to taking photographs.
9. Investigator to complete assessment of the subject's bilateral LCL severity at **CCI** maximum smile using the 4-point Photographic Scale (LCL-ILA). (Section [7.1.1](#) and [Appendix 1](#))
10. Investigator to complete assessment of the subject's GL severity at **CCI** maximum frown using the 4-point Photographic Scale (GL-ILA). (Section [7.1.3](#) and [Appendix 3](#))
11. Schedule the next monthly visit (\pm 5 days).

8.1.7 Month 6/Visit 10 or Early Termination visit (\pm 5 days)

At the Final/ET, the Investigator or designee will:

 GALDERMA	Title 43QMI902 Clinical Study Protocol - QM1114 - LCL and GL	Doc id MA-40371
--	---	----------------------------------

1. Ask the subject about AEs using an open-ended question, such as "Have you noticed any change in your health since the last visit?" Record all events, as appropriate.
2. Ask the subject about any changes in his/her concomitant therapies/procedures (added, removed or changed) since the previous visit. Record all changes.
3. Instruct the subject on how to complete the LCL-SLA at **CCI** maximum smile. Subject to complete self-assessment of bilateral LCL severity using the 4-point Photographic Scale. (Section [7.1.2](#) and [Appendix 2](#))
4. Instruct the subject on how to complete the GL-SLA at maximum frown Subject to complete self-assessment of GL severity using the Static 4-point Categorical Scale. (Section [7.1.4](#))
5. **CCI**
- 6.
- 7.
8. Obtain the subject's vital signs (blood pressure, heart rate, and respiratory rate). Vital signs are to be taken seated after 10 minutes rest (Section [7.2.2](#)).
9. Obtain 12-lead ECG recording after the subject has been resting in a supine position for at least 10 minutes ([Section 7.2.3](#)).
10. Collect blood sample (chemistry and hematology) for analysis at the central laboratory ([Section 7.2.4](#)).
11. Collect blood sample for neutralizing antibody testing ([Section 7.2.5](#)).
12. If the subject is a female of childbearing potential, collect urine for UPT and complete pregnancy test (see laboratory manual for additional procedures). Document the result.
13. Take subject photographs (refer to photo manual for complete instructions). If the subject is wearing make-up, instruct the subject to remove it prior to taking photographs.
14. Investigator to complete assessment of the subject's bilateral LCL severity at **CCI** maximum smile using the 4-point Photographic Scale (LCL-ILA). (Section [7.1.1](#) and [Appendix 1](#))
15. Investigator to complete assessment of the subject's glabellar line severity at **CCI** maximum frown using the 4-point Photographic Scale (GL-ILA). (Section [7.1.3](#) and [Appendix 3](#))
16. Investigator to perform a focused PE. ([Appendix 6](#))
17. Exit the subject from the study.

8.2 Unscheduled Visits

When necessary, unscheduled visits may be conducted, in particular if an AE occurs and needs to be assessed and/or treated.

 GALDERMA	Title 43QMI902 Clinical Study Protocol - QM1114 - LCL and GL	Doc id MA-40371
--	---	----------------------------------

8.3 Subject Instructions

CCI

Subjects will be advised that any facial make-up will need to be removed before taking study photographs.

Subjects will also be advised of post-treatment care instructions as outlined in Section [6.1.7.2](#).

9. STATISTICAL METHODS PLANNED

9.1 Statistical and Analytical Plans

A Statistical Analysis Plan (SAP) will be developed as a separate document. The SAP will contain a more detailed and technical description of specific data conventions, calculations and of statistical procedures for executing the analyses that are specified in the sections of the clinical study protocol below. The SAP will be finalized prior to database lock.

A separate SAP for EU will be created. The EU SAP will include a responder definition for the primary endpoint according to the EU requirement.

Any change made to the finalized SAP will be documented in the Clinical Study Report (CSR).

9.1.1 Data Transformations

CCI

For antibody testing results, log transformation might be used as necessary.

9.1.2 Populations Analyzed and Evaluability

The statistical analyses will be performed based on the following subject populations.

9.1.2.1 *Modified Intent-to-treat (mITT) Efficacy Population*

The modified Intention-to-treat (ITT) population includes all subjects who are randomized and dispensed the investigational product, and will be analyzed according to the randomization scheme; subjects with a photographic and categorical scale Month 1 assessment via a remote visit will be excluded from the mITT. The mITT population will be used for primary efficacy analysis.

 GALDERMA	Title 43QMI902 Clinical Study Protocol - QM1114 - LCL and GL	Doc id MA-40371
--	---	----------------------------------

Effective date: 2020-06-09 07:02

Effective

Version: 4.0

9.1.2.2 *Intent-to-treat (ITT) Efficacy Population*

The Intention-to-treat (ITT) population includes all subjects who are randomized and dispensed the investigational product, and will be analyzed according to the randomization scheme. All secondary efficacy **CCI** variables will be analyzed based on the ITT population, as well as a sensitivity analysis of the primary efficacy endpoint.

9.1.2.3 *Per-protocol (PP) Efficacy Population*

The Per Protocol (PP) population is a subset of the mITT subjects who have no protocol deviations that are considered to have a substantial impact on the primary efficacy outcome. If the PP population contains less than 90% of the subjects in mITT, a sensitivity analysis of the primary efficacy endpoint will be performed based on the PP population.

9.1.2.4 *Safety Population*

The safety population includes all subjects who were administered the study product, and will be analyzed according to as-treated principle. All safety data will be summarized descriptively based on the safety population.

9.1.2.5 *Imputation of Missing Data*

The Observed Cases (OC) will be used for all safety analyses as well as the secondary **CCI** efficacy analyses. The primary efficacy analysis will be performed using multiple imputation (MI) and repeated using baseline observation carried forward (BOCF) for missing values. If deemed necessary, any analyses may be repeated using OC, BOCF, or MI as appropriate.

9.1.3 *Data Presentation and Graphics*

All statistical analyses, including summary tables and data listings, will be performed using the SAS® system (version 9).

All efficacy, safety and baseline characteristics variables will be presented using descriptive statistics within each treatment group, and graphs as appropriate. Continuous data will be summarized using n (number of observations), mean, standard deviation, median, minimum and maximum value, while categorical data will be presented by n and percentages. All data will also be listed in subject data listings.

Subject disposition, completion and discontinuation by study visit, protocol deviations, demographics and baseline characteristics, medical history, medical and surgical procedures, prior and concomitant medications, will be summarized by treatment group.

For analysis of duration of response and time to onset of treatment response, Kaplan-Meier plots and estimates of the median event times will be used.

 GALDERMA	Title 43QMI902 Clinical Study Protocol - QM1114 - LCL and GL	Doc id MA-40371
--	---	----------------------------------

9.1.3.1 *Subgroup Analysis*

Analysis on the proportion of composite responders at Month 1 as measured by the ILA and the SLA at maximum smile and maximum frown, separately, will be performed in the following subgroups:

- Gender
- Baseline severity score of the ILA of LCL severity at maximum smile
- Baseline severity score of the ILA of GL at maximum frown
- Previous treatment with BoNT-A
- Fitzpatrick skin type

For duration of response, a subgroup analysis using only subjects with at least 2 point improvement on the LCL-ILA and GL-ILA, respectively will be conducted. Thus, duration of response will be analyzed based on the full ITT population as well as a subgroup analysis.

9.1.3.2 *Safety Analysis*

All treatment related TEAEs by maximum intensity, treatment unrelated TEAEs by maximum intensity, treatment emergent SAEs by causality and maximum intensity, and action taken of treatment related TEAEs will be summarized by SOC and PT including number of subjects with at least one event, percentages, and number of events. All related TEAEs will also be summarized by time to onset and duration. In addition, a short summary of these presentations will be provided.

Data for hematology, blood chemistry, antibodies, and vital signs will be summarized by descriptive statistics with the value at each visit as well as the change from baseline. Results of ECGs will be summarized descriptively. The results of the urine pregnancy tests will be listed

9.1.4 **Withdrawals and Deviations**

All withdrawn subjects will be listed individually, including at least subject number, date and reason for withdrawal, and last visit performed.

Subjects with CSP deviations will be listed individually, including subject number and observed deviation. They will also be summarized by study center and in total (by treatment group and overall). Depending on the seriousness of the deviation, the subject might be excluded from the PP population, which shall be documented prior to database lock.

9.1.5 **Inferential Statistical Analyses**

The primary efficacy endpoints will be a composite responder rate at Month 1 based on the ILA and SLA of LCL severity at maximum smile, and ILA and SLA of GL severity at maximum frown. A responder is defined as a subject who achieves grade/level 0 or 1 and at least 2 grades improvement from baseline, on both the Investigator and subject scale concurrently. The null hypothesis of no

 GALDERMA	Title 43QMI902 Clinical Study Protocol - QM1114 - LCL and GL	Doc id MA-40371
--	---	----------------------------------

relationship between treatment and responder rate will be tested against the alternative hypothesis that there is a relationship between treatment and responder rate (for each of the four comparisons). The responder rates of QM1114-DP and placebo will be compared using Cochran-Mantel-Haenszel test (stratified by center) at 5% significance level (2-sided). Depending of the number of centers, pooling of centers might be needed. The group treated in one rhytid area (LCL or GL) alone and the group with concurrent LCL and GL treatment will be analyzed separately. To control the type I error rate among the 4 primary efficacy comparisons, the fixed sequence procedure will be used which requires no adjustment to the level of significance. The comparisons will be done in the following order:

1. GL alone group vs placebo on the GL scale
2. GL + LCL group vs placebo on the GL scale
3. LCL alone group vs placebo on the LCL scale
4. GL + LCL group vs placebo on the LCL scale

The analysis of the primary efficacy endpoint will be based on the mITT population. A sensitivity analysis of the primary efficacy endpoint will be performed using the ITT population.

For registration of the product in the EU, a different definition of the primary efficacy endpoints will be used.

All other endpoints will be analyzed descriptively. For efficacy, percentages of subjects over time will be presented in graphs. Duration of treatment effect and time to onset will be analyzed with Kaplan-Meier methods.

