14.2.12.1	Percentage of Subjects with ≥ 2 Grade Improvement using the GL-ILA at Maximum Frown at Each Visit	ITT	U
CCI			
14.2.12.3	Percentage of Subjects with ≥ 2 Grade Improvement using the GL-SLA at Maximum Frown at Each Visit	ITT	R
14.2.13.1	Percentage of Subjects with ≥ 2 Grade Improvement using the LCL-ILA at Maximum Smile at Each Visit	ITT	R
CCI			
14.2.13.3	Percentage of Subjects with ≥ 2 Grade Improvement using the LCL-SLA at Maximum Smile at Each Visit	ITT	R
CCI			
14.2.14.1	Time to Return to Baseline Score on GL-ILA and GL-SLA at Maximum Frown	ITT	U
14.2.14.2	Time to Return to Baseline Score on GL-ILA and GL-SLA at Maximum Frown for Subjects with ≥ 2 Grade Improvement at Month 1 GL-ILA at Maximum Frown	ITT	R
14.2.15.1	Time to Loss of Grade 0 or 1 on the GL-ILA and GL-SLA at Maximum Frown	ITT	R
14.2.15.2	Time to Loss of Grade 0 or 1 on the GL-ILA and GL-SLA at Maximum Frown for Subjects with ≥ 2 Grade Improvement at Month 1 GL-ILA at Maximum Frown	ITT	R
14.2.16.1	Time to Return to Baseline Score on LCL-ILA and LCL-SLA at Maximum Smile	ITT	U
14.2.16.2	Time to Return to Baseline Score on LCL-ILA and LCL-SLA at Maximum Smile for Subjects with ≥ 2 Grade Improvement at Month 1 LCL-ILA at Maximum Smile	ITT	R

Effective date: 2021-02-05 13:16

Effective date:

Effective

Version: 1.0

Table Number	Table Title	Analysis Population	(U)unique/ (R)repeat
14.2.17.1	Time to Loss of Grade 0 or 1 on the LCL-ILA and LCL-SLA at Maximum Smile	ITT	R
14.2.17.2	Time to Loss of Grade 0 or 1 on the LCL-ILA and LCL-SLA at Maximum Smile for Subjects with ≥ 2 Grade Improvement at Month 1 LCL-ILA at Maximum Smile	ITT	R
CCI			

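### Duration of response is planned in the whole ITT set and in a subset picked on the investigator scale alone, so results that use the subject scale can include subjects with no subject-scale response to lose

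*Protocol*

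**What the plan says.** **Method.** Protocol 9.1.3 gives the estimator: "For analysis of duration of response and time to onset of treatment response, Kaplan-Meier plots and estimates of the median event times will be used". Protocol 9.1.5 makes everything beyond the four primary comparisons descriptive.

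**Populations.** Protocol 9.1.3.1 names two. The first is the full ITT set: "Thus, duration of response will be analyzed based on the full ITT population as well as a subgroup analysis". Under Protocol 9.1.2.2, ITT means randomized and dispensed product, with no condition on response. The second is a subset: "a subgroup analysis using only subjects with at least 2 point improvement on the LCL-ILA and GL-ILA, respectively will be conducted". The protocol names no visit for that improvement; the SAP table titles set it at Month 1.

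**Events.** SAP 4.1 lists two types for each area:
- Return to baseline, for example "Time to Return to Baseline Score on GL-ILA and GL-SLA at Maximum Frown" (14.2.14.1; LCL counterpart 14.2.16.1).
- Loss of response, for example "Time to Loss of Grade 0 or 1 on the GL-ILA and GL-SLA at Maximum Frown" (14.2.15.1) and "Time to Loss of Grade 0 or 1 on the LCL-ILA and LCL-SLA at Maximum Smile" (14.2.17.1).

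Each is repeated in the ILA-selected subset (14.2.14.2, 14.2.15.2, 14.2.16.2, 14.2.17.2), for example "Time to Loss of Grade 0 or 1 on the GL-ILA and GL-SLA at Maximum Frown for Subjects with ≥ 2 Grade Improvement", where the title goes on to specify the Month 1 GL-ILA. Figures 6.1.1 to 7.2.2 in SAP 4.3 follow the same pattern.

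**The trial's own responder.** SAP 1.4.1 requires grade 0 or 1 and at least 2 grades of improvement on both scales, and on both sides for LCL. No visible duration table or figure uses that definition.

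**The concern.** Protocol 5.2.1 requires grade 2 or 3 at entry on all four scales. A subject who never improves therefore has no grade 0 or 1 to lose and never left baseline. A Kaplan-Meier median over the whole ITT set may then mix how many subjects respond with how long a response lasts. Placebo shows this most clearly: Protocol 1.3 expects no clinical benefit there, so a placebo median labelled as duration of response would say little about duration.

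The subset is meant to deal with this, but it selects on one scale while the titles name two. A subject whom the investigator rates from 3 to 1, and who self-rates 2 throughout, qualifies for the subset without ever holding subject grade 0 or 1. At stake is how the reported medians are read. No hypothesis test is affected.

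**Working it through.** The documents give no event count, power or target median for duration, so there is no planned figure to reproduce. The responder-rate assumptions are redacted. What follows is logic, then illustration.

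**1. What the subset guarantees.** From baseline 2, a 2-grade improvement gives grade 0. From baseline 3, an improvement of 2 or more grades gives 1 or 0. Every member therefore holds ILA grade 0 or 1 at Month 1 and is below baseline on the ILA. Nothing follows for the SLA.

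**2. ITT curve.** Let r be the share who respond. Let responders' time to loss be Weibull with median m and shape k. Assume m = 5 months, inside the 4 to 6 months that Protocol 1.1 gives as the usual persistence of effect. There are three ways to treat never-responders:
- Event at the start: r·S(t) = 0.5, so t = m·[ln(r/0.5)/ln 2]^(1/k). The median is 0 if r ≤ 0.5.
- Event-free to the end of follow-up: r·S(t) + (1 − r) = 0.5, so t = m·[−ln((r − 0.5)/r)/ln 2]^(1/k).
- Censored at time 0 or left out: the median stays at m.

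For r = 0.8 and k = 3, the first gives 5 × (0.4700/0.6931)^(1/3) = 4.39 months. The second gives 5 × (0.9808/0.6931)^(1/3) = 5.61 months.

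| r | Event at start, k = 1 to 3 | Event-free to end, k = 3 | Left out |
|---|---|---|---|
| 0.9 | 4.24–4.73 | 5.27 | 5.00 |
| 0.8 | 3.39–4.39 | 5.61 | 5.00 |
| 0.7 | 2.43–3.93 | 6.09 (just past Month 6) | 5.00 |
| 0.6 | 1.32–3.20 | 6.86 (not reached by Month 6) | 5.00 |
| ≤ 0.5 | 0 | not reached | 5.00 |

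The direction of the shift depends on the coding, and one coding gives no shift.

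**3. ILA-selected subset.** Let q be the share of the subset who also respond on the SLA. This was simulated with 400,000 subjects, Weibull shape 3 and a 5-month median on each scale. Subjects without an SLA response were given SLA loss at time 0. The scales were linked through normal scores with correlation 0 or 0.7; ranges cover both. Medians are in months.

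| Reading of the event | q = 1.0 | q = 0.9 | q = 0.8 | q = 0.7 |
|---|---|---|---|---|
| ILA alone | 5.0 | 5.0 | 5.0 | 5.0 |
| SLA alone | 5.00 | 4.73 | 4.39 | 3.93–3.94 |
| Loss on either scale | 3.97–4.42 | 3.76–4.17 | 3.49–3.85 | 3.12–3.42 |
| Loss on both scales | 5.59–6.04 | 5.54–5.97 | 5.48–5.88 | 5.42–5.78 |

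Falls at q = 0.8 against q = 1:
- SLA alone: 5.00 − 4.39 = 0.61.
- Either scale: 3.97 − 3.49 = 0.48 to 4.42 − 3.85 = 0.57.
- Both scales: 5.59 − 5.48 = 0.11 to 6.04 − 5.88 = 0.16.
- ILA alone: none.

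These are continuous-time medians. With monthly visits the reported values would move in visit steps.

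**The case against.** The strongest objection is that the decisive definitions may be redacted. The time origin, the risk set, the handling of never-responders and the meaning of the two-scale titles could all lie in blacked-out SAP endpoint and analysis text. That stands. Their absence from the visible text is not an omission in the plan.

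A reader might go further and infer four things that the documents do not support:
- **The median counts non-responders whichever way they are coded.** It does not if they are left out or censored at time 0.
- **Loss is judged jointly on both scales.** The titles fit each scale reported separately, loss on either, or loss on both.
- **The subset as a whole does not match its event.** For an ILA result it matches exactly, by step 1.
- **The ITT analysis should be demoted.** It keeps the randomised comparison and is a legitimate summary of time with effect. A responder subset conditions on a post-randomisation outcome.

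It is also fair that the ILA subset already answers part of the ITT concern. Composite response on both scales is tabulated at every visit (SAP tables 14.2.1.11 and 14.2.2.11). Duration is not among the visible secondary endpoints. None of this supplies a visible duration result restricted to subjects who responded on the subject scale.

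**Conclusion.** The point holds in a limited form. On the visible text, the ITT curve describes time with effect in all treated subjects and should not be read as duration among responders, unless redacted text removes never-responders from the risk set. The ILA-selected subset secures an investigator-scale response but not a subject-scale one.

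The mismatch is moderate for SLA alone or loss on either scale, small if both scales must be lost, and nil for ILA alone. The sizes rest on assumed response shares, a 5-month median, Weibull curves and loss at time 0 for subjects without an SLA response. The documents supply no response rates, so the sizes show sensitivity and do not predict the trial's result. The primary comparisons and the type I error are untouched.

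**What to change.** 1. In tables 14.2.14.2, 14.2.15.2, 14.2.16.2 and 14.2.17.2 and figures 6.2.1, 6.2.2, 7.2.1 and 7.2.2, add or substitute a subset of subjects who responded at Month 1 on the same scale or scales used to judge loss. For a two-scale event this is the composite responder of SAP 1.4.1, with both sides for LCL. For an SLA-only result, select on the SLA. The present ILA subset already suits an ILA-only result.
2. Keep the ITT tables and figures, label them as time with effect in all treated subjects, and print the responder proportion for each arm beside its median.
3. If the redacted text does not already do so, state the time origin, the handling of never-responders, and whether the two-scale titles mean each, either or both scales.

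The cost is a subset flag, table and figure titles and some SAP wording. The Month 1 flags needed are already derived for the primary endpoint and in SAP 1.3.1 to 1.3.4, so no new data are needed. The downsides are fewer subjects, a nearly empty placebo curve, and selection on a post-randomisation outcome. The subset result must therefore stay descriptive and should not be used to compare arms.
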